8.5.3.2 Vital Signs

Measurements for vital signs as well as changes from baseline will be summarized with descriptive statistics: mean, standard deviation, minimum, median, and maximum

Protocol Version: 7.0

INO-4800	COVID19-311
Inovio Pharmaceuticals, Inc.	Clinical Protocol

values by time point and treatment arm, for the Safety population. Baseline is defined as the last measurement prior to the first treatment administration. These summaries will be performed according to Phase. For the Phase 2 segment, the analyses listed above will also be performed according to prior receipt of any non-study prophylactic COVID-19 vaccine. For the Phase 3 segment, the analyses listed above will also be performed according to SARS-CoV-2 serostatus at baseline.

8.5.4 **DISPOSITION**

Disposition will be summarized by treatment arm for the ITT population and will include the number and percentage randomized, the number and percentage who received each dose and the number who completed the trial. The number and percentage of subjects who discontinued will be summarized overall and by reason. The number in each analysis population will also be presented. These summaries will be performed according to Phase. For the Phase 3 segment, the analyses listed above will also be performed according to SARS-CoV-2 serostatus at baseline.

$8.5.5\,\mbox{Demographic}$ and Other Baseline Characteristics

8.5.5.1 Demographics

Demographic data will be summarized with descriptive statistics: mean standard deviation, minimum, median, and maximum values for continuous variables, and percentages for categorical variables, by treatment arm, for the ITT and PP populations. These summaries will be performed according to Phase. For the Phase 3 segment, the analyses listed above will also be performed according to SARS-CoV-2 serostatus at baseline.

8.5.5.2 Prior Medications

Prior medications are those that were used before the start of the trial (prior to Day 0). Partial stop dates of prior medications will be assumed to be the latest possible date consistent with the partial date; start dates will not be imputed. Data for all prior medications will be summarized with percentages by treatment arm, for the ITT and PP populations. These summaries will be performed according to Phase. For the Phase 3 segment, the analyses listed above will also be performed according to SARS-CoV-2 serostatus at baseline.

8.5.6 INTERIM ANALYSES

For safety issues, the DSMB could recommend stopping enrollment at any time; no formal interim analysis will be performed for this purpose. The two-sided type I error of 0.05 will not be adjusted for possible early stopping due to this aspect.

For the Phase 2 segment, group-level unblinded summaries of the immunogenicity and safety data will be produced once Week 6 visit immunology data and Week 8 visit safety data are complete for all subjects who have not discontinued, while maintaining subject-level blinding. Long-term follow-up data will continue to be collected for all subjects who have not discontinued with remaining visits through the final visit. These summaries will allow the Sponsor to have results for the purposes of dose selection for the Phase 3 portion. No subject-level immunogenicity data will not be available in the clinical trial database until all other clinical trial data are finalized at the end of the trial. No safety summary will be provided if the total number of subjects who experience the event of interest is greater than 0 and the count of the number of subjects with the event in a given treatment group relative to the

INO-4800	COVID19-311
Inovio Pharmaceuticals, Inc.	Clinical Protocol

total produces a percentage less than 3%, for a given summary. The group-level unblinded production of the summaries will not include anyone directly involved with the trial or any additional unblinded personnel; only the external Contract Research Organization (CRO), ICON, which will already be providing unblinded summaries for the Data Safety Monitoring Board, will be utilized. Thus, the trial will remain blinded to the Sponsor with respect to subject treatment assignment.

8.5.7 MULTIPLICITY

Not applicable; there is one primary hypothesis that will be tested.

8.5.8 MISSING VALUES

Missing data will not be imputed.

For the ITT analyses of efficacy in the Phase 3 segment, subjects with missing or unevaluable data regarding case definition will be considered cases (failures).

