8.5.1 PRIMARY ANALYSIS

Phase 2 Segment

Post-baseline increases from baseline in interferon-γ ELISpot response magnitudes will be compared between treatment groups using differences in medians and associated non-parametric 95% CIs.

Post-baseline increases from baseline in neutralizing antibody response titers will be compared between treatment groups using ratios of geometric mean fold-rises and associated t-distribution based 95% CIs.

The summaries listed above will be stratified according to NP positive/negative status and according to prior receipt of any non-study prophylactic COVID-19 vaccine of the subjects. Valid samples for statistical analysis purposes will be those collected: at least 6 and no more than 30 days after Dose 2 for the Week 6 timepoint; at least 174 and no more than 198 days after Dose 2 for the Week 30 timepoint; and at least 356 and no more than 380

INO-4800	COVID19-311
Inovio Pharmaceuticals, Inc.	Clinical Protocol

days after Dose 2 for the Week 56 timepoint. Baseline is defined as the last measurement prior to the first treatment administration.

The PP population will be used for these immunogenicity analyses.

Phase 3 Segment

Among subjects who are SARS-CoV-2 seronegative and RT-PCR negative at baseline, the primary hypothesis of relative efficacy greater than 30% will be tested with H₀: $p \ge 0.70/(0.70+k) vs$. H₁: p < 0.70/(0.70+k), where p is the true proportion of subjects with severe disease who receive INO-4800 relative to the total number of subjects with severe disease, and k is the total amount of follow-up time in the placebo group divided by the total amount of follow-up time in the INO-4800 group.

A p-value for this hypothesis test and corresponding confidence interval will be computed based on the exact binomial method of Clopper-Pearson. Success will be concluded if the one-sided p-value is <0.025 and the corresponding lower bound of the two-sided 95% Cl for efficacy exceeds 30%.

For calculating k, an individual subject's follow-up time is either:

- the date of first disease diagnosis date of the start of surveillance period +1 (for subjects who are cases), or
- the date of last follow-up date of the start of surveillance period +1 (for subjects who are non-cases).

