This methodology is based on the following. Assuming that the number of subjects who are cases in the INO-4800 group follows a Poisson distribution with parameter λ_v and the number of subjects who are cases in the placebo group follows a Poisson distribution with parameter λ_c , then conditional on total number of subjects with cases, t, the number of subjects who are cases in the INO-4800 group follows a binomial distribution with parameters (t, $p = \lambda_v/(\lambda_v + \lambda_c)$). The relationship between p and efficacy is: efficacy = (1-(1+k)p)/(1-p). Therefore, testing efficacy > 30% corresponds to testing p < 0.70/(0.70+k). Similarly, the confidence interval for efficacy is (1-(1+k)UB_p)/(1-UB_p), (1-(1+k)LB_p)/(1-LB_p), where UB and LB are the Clopper-Pearson upper and lower limits for the proportion.

The efficacy time frame is defined by symptoms beginning at any time starting from 14 days after Dose 2 and ending 12 months after Dose 2. Subjects identified as cases that started prior to this time point will be excluded. Subjects with multiple instances meeting the case definition will be counted only once, using the first such instance.

The PP population will be primary for the analysis of efficacy in this trial. Efficacy analysis using the mITT population will also be conducted counting cases from 14 days postdose 1 as a supportive analysis. The ITT population will also be used for a supportive analysis counting cases starting from randomization.

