8.5.9.3 Concomitant Medications

Concomitant medications are those used during the course of the trial (on or after Day 0). Partial stop dates of concomitant medications will be assumed to be the latest possible date consistent with the partial date; start dates will not be imputed. Data for all concomitant medications will be summarized with percentages by treatment arm, for the ITT and PP populations. These summaries will be performed according to Phase. For the Phase 3 segment, the analyses listed above will also be performed according to SARS-CoV-2 serostatus at baseline.

8.6 **SAMPLE SIZE/POWER**

Phase 3 segment: The trial is case-driven. A total of 17 observed severe cases among baseline SARS-CoV-2 seronegative and RT-PCR negative subjects will be required to provide 90% power to declare the vaccine efficacious (>30%), assuming a true efficacy of 90% and utilizing the methodology described in Section 8.5.1. A sample size of 10,002 baseline SARS-CoV-2 seronegative subjects is expected to be required to achieve this number of cases assuming an underlying attack rate of approximately 0.4%.

8.7 **RANDOMIZATION AND BLINDING**

Phase 2 Segment

Subjects will be randomized (3 INO-4800 1.0 mg, one injection: 3 INO-4800 2.0 mg, two injections:1 Placebo, one injection: 1 Placebo, two injections).

The study is blinded. It is double-blinded within dose group. Randomization and blinding will avoid bias in the assignment of subjects to treatment, increase the likelihood that known and unknown subject attributes (e.g., demographics and other baseline characteristics) are evenly balanced between treatment groups, and enable valid statistical comparisons between treatment groups. Subject treatment assignments will be unblinded after Phase 2 subjects have reached the Week 30 visit.

Phase 3 Segment

Subjects will be randomized (2 INO-4800:1 Placebo). Randomization will be stratified according to two factors, each with two levels: a) age-group age category (18-50 years vs. ≥51 years) on Day 0, and b) presence or absence on Day 0 of underlying medical conditions that increase risk of severe COVID-19 disease, per US CDC criteria.

The study is double-blinded. Randomization and blinding will avoid bias in the assignment of subjects to treatment, increase the likelihood that known and unknown subject attributes

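### The ITT rule that counts missing case data as cases (Section 8.5.8) does not suit the rare severe endpoint of version 7.0 and can make the supportive ITT estimate misleading

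*Protocol*

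**What the plan says.** All references are to protocol version 7.0 unless stated.

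- Section 8.5.8 opens with a general rule, "Missing data will not be imputed", and then makes an exception for the Phase 3 ITT efficacy analyses: "subjects with missing or unevaluable data regarding case definition will be considered cases (failures".
- Section 8.5.1 gives the ITT analysis its role: "The ITT population will also be used for a supportive analysis counting cases starting from randomization". The per-protocol (PP) population is primary. The mITT population, which is everyone who received at least one dose, gives a second supportive analysis. The failure rule names only ITT.
- Section 8.6 sets the scale of the endpoint: "A total of 17 observed severe cases among baseline SARS-CoV-2 seronegative and RT-PCR negative subjects will be required to" give 90% power, "assuming a true efficacy of 90% and utilizing the methodology described in Section 8.5.1". It expects this from 10,002 seronegative subjects at an attack rate of about 0.4%.
- Section 8.5.8 of version 6.0 has the same failure rule. There the primary endpoint was any virologically confirmed COVID-19, with 149 cases planned at a 3.7% attack rate.

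**The concern.** Treating missing as failure is a tolerable worst case when the outcome is common, because the imputed events are a modest share of the total. Version 7.0 made the primary endpoint rare and left the rule as it was. Each imputed subject is assigned a 100% risk of severe disease, where the plan expects 0.4% on placebo and 0.04% on vaccine. If imputed subjects fall 2:1, as randomisation would place them, they pull the estimate towards no effect.

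The stake is interpretive. The PP set drops anyone with a protocol violation, so a reader will look to ITT to see whether those exclusions drive the result. An ITT estimate made mostly of imputed cases cannot answer that question. Setting it aside after unblinding would look post hoc.

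**Working it through.** **Inputs.** Arms of 6668 and 3334 seronegative subjects (Table 2); placebo attack rate 0.4% and true efficacy 90% (Section 8.6), so 0.04% on vaccine; k = 0.5 from 2:1 allocation with similar follow-up; null efficacy 30%, one-sided 0.025, exact binomial with Clopper-Pearson limits (Section 8.5.1). The missing rate m is not in the protocol and is an assumption, shown as a range.

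**The plan's own figure.** Under the null, p0 = 0.70/(0.70 + 0.5) = 0.583. Under 90% efficacy, p1 = 0.10/(0.10 + 0.5) = 0.167. With 17 cases the test rejects at 5 or fewer in the vaccine arm (actual alpha 0.0153, power 95.0%). With 16 cases power is 88.7%. So 17 is reproduced as the count from which exact power stays above 90%.

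Expected cases are 3334 × 0.004 = 13.3 on placebo and 6668 × 0.0004 = 2.7 on vaccine, 16.0 in all. Seventeen needs an attack rate of 0.425%, consistent with the stated approximate 0.4%.

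**The ITT estimate under the rule.** Cases per arm = n × [rate × (1 − m) + m]. Section 8.5.1's efficacy formula reduces to 1 − k × (vaccine cases / placebo cases). With equal m in both arms:

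| m | Subjects imputed | Vaccine : placebo cases | ITT efficacy | 95% CI |
|---|---|---|---|---|
| 0 | 0 | 2.7 : 13.3 | 90% | 58% to 98% |
| 0.1% | 10 | 9.3 : 16.7 | 72% | 37% to 90% |
| 0.2% | 20 | 16.0 : 20.0 | 60% | 19% to 81% |
| 0.5% | 50 | 36.0 : 29.9 | 40% | -1% to 64% |
| 1% | 100 | 69.3 : 46.5 | 25.5% | -9% to 50% |
| 5% | 500 | 335.9 : 179.4 | 6.4% | -13% to 22% |
| 10% | 1000 | 669.2 : 345.4 | 3.1% | -10% to 15% |

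Intervals use counts rounded to whole cases. A perfect vaccine would show 28% at 1% missing and 7.1% at 5%.

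**Thresholds.** The estimate is 0.0036(1 − m) / [0.004(1 − m) + m]. It falls below 50% at m = 0.32%, which is 0.0032 × 10,002, or about 32 subjects, and below 30% at m = 0.79%, about 79 subjects. The lower confidence limit is 37% at 0.10% missing and 22% at 0.15%, so it crosses 30% with 10 to 15 imputed subjects.

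**Unequal missingness.** At 5% on vaccine and 10% on placebo, efficacy = 1 − (0.05038 / 0.1036) = 51%. Reversed, it is 1 − (0.10036 / 0.0538) = -87%. Both lie close to 1 minus the ratio of missing rates (50% and -100%).

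**Version 6.0 for comparison.** At a 3.7% attack rate and 60% efficacy, 5% missing gives 0.037 × 0.6 × 0.95 / (0.037 × 0.95 + 0.05) = 25%. The dilution existed then, but the change of endpoint made it far worse.

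The true-case counts refer to the window from 14 days after dose 2. ITT counts from randomisation, so there may be slightly more, which does not change the picture.

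**The case against.** **The missing rate.** The protocol gives none, and at 0.1% missing the estimate is still 72%. A reader might infer that the ITT estimate goes to zero whatever the vaccine does. The documents do not support that: near-zero efficacy appears only at assumed rates of about 5% and above, and only with similar missingness in the two arms. This objection stands, and the size must be stated conditionally.

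**A narrower reading.** The rule concerns data on the case definition, and Section 8.5.1 already lets non-cases contribute time to their last follow-up. A dropout with no suspected illness could be read as a censored non-case, leaving only events the Endpoint Adjudication Committee (EAC) could not resolve. That reading is reasonable, but the text does not choose it. Nor does it remove the problem: about 32 such subjects split 2:1 (21 and 11) still bring the estimate to 50%.

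**Mild illness.** A reader might infer that a trivial illness with a lost swab becomes a severe case. Section 3.7.1.1 requires confirmed disease and a severity criterion, so an illness known to meet no severity criterion is an evaluable severe non-case.

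**Contradiction.** The two sentences of Section 8.5.8 can be read as contradictory. They are better read as a general rule with a stated exception.

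**Reach.** ITT is only supportive. Success rests on the PP test, so the 17-case power is untouched. mITT is outside the rule and should retain nearly everyone, because randomisation is a Day 0 step before dosing (Section 6.1.2.1). This also stands.

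**Conclusion.** The point holds as a defect in one supportive analysis. Applied as written, the rule can leave an ITT estimate that reflects retention more than vaccine effect. With equal missingness, a true efficacy of 90% and the plan's 0.4% attack rate, imputed cases outnumber the 16 expected real ones from about 0.2% missing (20 subjects), and at 1% there are about 100 of them. Rates of that order are an assumption, though a modest one for 56 weeks of follow-up with a procedure for loss to follow-up in Section 4.3.

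It should not be taken to mean that the primary analysis or its power is compromised, or that no other supportive check exists. What is lost is the one analysis that keeps every randomised subject, and it could falsely appear to contradict a positive PP result.

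**What to change.** Delete the failure sentence from Section 8.5.8. State instead that the ITT analysis counts only EAC-confirmed cases from randomisation, and that all other subjects contribute follow-up time to their last evaluable contact, in line with Section 8.5.1's treatment of non-cases. mITT needs no change.

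Censoring assumes that missingness is unrelated to severe disease. If a stress test of that assumption is wanted, specify a tipping-point analysis that gives missing subjects plausible arm-specific severe attack rates, for example 1 to 5 times the observed rate.

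The cost is one sentence replaced before unblinding, with no new data, visits or subjects.

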8.5.9 EXPLORATORY ANALYSES

8.5.9.1 Efficacy

Phase 3 segment

The exploratory efficacy endpoints will be analyzed in the same manner as the primary hypothesis, but without the hypothesis test p-value.

8.5.9.2 Immunogenicity

Phase 2 segment

Post-baseline increases from baseline in cellular response magnitudes will be compared between treatment groups using differences in medians and associated non-parametric 95% CIs.

The summaries listed above will be stratified according to NP positive/negative status and according to prior receipt of any non-study prophylactic COVID-19 vaccine of the subjects.

Valid samples for statistical analysis purposes will be those collected: at least 6 and no more than 30 days after Dose 2 for the Week 6 timepoint; at least 174 and no more than 198 days after Dose 2 for the Week 30 timepoint; and at least 356 and no more than 380 days after Dose 2 for the Week 56 timepoint. Baseline is defined as the last measurement prior to the first treatment administration.

The PP population will be used for immunogenicity analyses.

Phase 3 Segment

Post-baseline increases in antibody titers from ELISA will be compared between treatment groups using ratios of geometric mean fold-rises and associated 95% t-distribution based CIs.

Post-baseline increases from baseline in cellular response magnitudes will be compared between treatment groups using differences in medians and associated non-parametric 95% CIs.

INO-4800	COVID19-311
Inovio Pharmaceuticals, Inc.	Clinical Protocol

Post-baseline increases from baseline in neutralizing antibody response titers will be compared between treatment groups using ratios of geometric mean fold-rises and associated t-distribution based 95% CIs.

The summaries listed above will be stratified according to disease status of the subjects.

Valid samples for statistical analysis purposes will be those collected: at least 6 and no more than 30 days after Dose 2 for the Week 6 timepoint; at least 174 and no more than 198 days after Dose 2 for the Week 30 timepoint; and at least 356 and no more than 380 days after Dose 2 for the Week 56 timepoint. Baseline is defined as the last measurement prior to the first treatment administration.

The PP population will be used for immunogenicity analyses.

8.5.9.3 Concomitant Medications

Concomitant medications are those used during the course of the trial (on or after Day 0). Partial stop dates of concomitant medications will be assumed to be the latest possible date consistent with the partial date; start dates will not be imputed. Data for all concomitant medications will be summarized with percentages by treatment arm, for the ITT and PP populations. These summaries will be performed according to Phase. For the Phase 3 segment, the analyses listed above will also be performed according to SARS-CoV-2 serostatus at baseline.

8.6 **SAMPLE SIZE/POWER**

Phase 3 segment: The trial is case-driven. A total of 17 observed severe cases among baseline SARS-CoV-2 seronegative and RT-PCR negative subjects will be required to provide 90% power to declare the vaccine efficacious (>30%), assuming a true efficacy of 90% and utilizing the methodology described in Section 8.5.1. A sample size of 10,002 baseline SARS-CoV-2 seronegative subjects is expected to be required to achieve this number of cases assuming an underlying attack rate of approximately 0.4%.

8.7 **RANDOMIZATION AND BLINDING**

Phase 2 Segment

Subjects will be randomized (3 INO-4800 1.0 mg, one injection: 3 INO-4800 2.0 mg, two injections:1 Placebo, one injection: 1 Placebo, two injections).

The study is blinded. It is double-blinded within dose group. Randomization and blinding will avoid bias in the assignment of subjects to treatment, increase the likelihood that known and unknown subject attributes (e.g., demographics and other baseline characteristics) are evenly balanced between treatment groups, and enable valid statistical comparisons between treatment groups. Subject treatment assignments will be unblinded after Phase 2 subjects have reached the Week 30 visit.

Phase 3 Segment

Subjects will be randomized (2 INO-4800:1 Placebo). Randomization will be stratified according to two factors, each with two levels: a) age-group age category (18-50 years vs. ≥51 years) on Day 0, and b) presence or absence on Day 0 of underlying medical conditions that increase risk of severe COVID-19 disease, per US CDC criteria.

The study is double-blinded. Randomization and blinding will avoid bias in the assignment of subjects to treatment, increase the likelihood that known and unknown subject attributes

(e.g., demographics and other baseline characteristics) are evenly balanced between treatment groups, and enable valid statistical comparisons between treatment groups.

9.0 **ETHICS**

9.1 INVESTIGATOR AND SPONSOR RESPONSIBILITIES

The Investigator and Sponsor are responsible for ensuring that the clinical trial is performed in accordance with the protocol, the principles of the Declaration of Helsinki, Good Clinical Practice (GCP) and applicable regulatory requirements.

9.2 INSTITUTIONAL REVIEW BOARD (IRB)/RESEARCH ETHICS BOARD (REB)/ETHICS COMMITTEE (EC)

The Investigator will commence the clinical trial after full approval of the protocol and adjunctive materials (e.g., ICF, advertising) has been obtained from the applicable IRB/REB/EC and a copy of IRB/REB/EC approval documentation has been received by the Sponsor.

Investigator responsibilities relevant to the IRB/REB/EC include the following:

- Submit continuing review reports to the IRB/REB/EC as required, and request rereview and approval of the clinical trial at least once a year during the conduct of the clinical trial;
- Notify the Sponsor immediately of any suspected unexpected adverse drug or device events/effects;
- Notify the IRB/REB/EC immediately if the Sponsor notifies the Investigator about any reportable safety events;
- Obtain approval from the IRB/REB/EC for protocol amendments and for revisions to the consent form or subject recruitment advertisements, as required;
- Submit reports on, and reviews of, the clinical trial and its progress to the IRB/REB/EC at intervals stipulated in their guidelines and in accordance with pertinent regulations and guidelines;
- Maintain a file of clinical trial-related information (refer to clinical trial files) that includes all correspondence with the IRB/REB/EC;
- Notify the IRB/REB/EC when the clinical trial is completed (i.e., after the last clinical trial visit of the final clinical trial subject);
- After clinical trial completion (within three [3] months is recommended), provide the IRB/REB/EC with a final report on the clinical trial.

Institutional Biosafety Committee (IBC)

The Investigator will undertake the trial after full approval of the protocol and adjunctive materials (e.g., pharmacy manual) has been obtained from the applicable IBC and a copy of this approval has been received by the Sponsor.

Investigator responsibilities relevant to the IBC include the following:

- Notify the Sponsor, IBC and NIH OSP within 30 days of any:
 - Substantial problems or violation of the NIH Guidelines
 - Significant research related accidents or illnesses

INO-4800	COVID19-311
Inovio Pharmaceuticals, Inc.	Clinical Protocol

• Notify the IBC to any changes to the research (dosage, procedure, etc.) or facility (new space, remodeling, etc.).

9.3 **PROTECTION OF HUMAN SUBJECTS**

